7.2.1.4 Assessment of Intensity

Intensity refers to the degree of discomfort or impairment associated with an event. The intensity of AEs is to be reported on the eCRF as mild, moderate, or severe, according to the definitions provided below. In addition, to maximize consistency in assessment, it is

recommended that the National Cancer Institute (NCI) Common Terminology Criteria for Adverse Events (CTCAE) scale be used.

Intensity	Corresponding NCI CTCAE Grade
Mild: awareness of a sign or symptom but easily tolerated	1
Moderate: discomfort sufficient to cause interference with normal daily activities	2
Severe: resulting in inability to do work or perform normal daily activities	3–5

7.2.1.5 Serious Adverse Events

An SAE is an adverse event occurring at any dose that results in any of the following outcomes:

- Death
- A life-threatening adverse event
- Inpatient hospitalization or prolongation of existing hospitalization
- A persistent or significant disability or incapacity
- A congenital anomaly in the offspring of a patient who received the study treatment
- An important medical event that does not result in death, is not life-threatening, and does not necessitate hospitalization but which in the investigator’s judgment may jeopardize the patient and may necessitate medical or surgical intervention to prevent one of those outcomes. Examples include allergic bronchospasm requiring intensive treatment in an emergency room or at home, blood dyscrasias or convulsions that do not result in inpatient hospitalization, or the development of drug dependency or treatment-related substance abuse.

Clarifications:

- “Life-threatening” means that the patient was, in the view of the investigator, at immediate risk of death from the event as it occurred. This definition does not include an event that, had it occurred in a more severe form, might have caused death.
- Hospitalization for elective treatment of a pre-existing condition that did not worsen during the study is not considered an AE.

- Complications that occur during hospitalization are AEs. If a complication prolongs hospitalization, the event is considered an SAE.
- “Inpatient” hospitalization means the patient has been formally admitted to a hospital for medical reasons. This may or may not be overnight. It does not include presentation at a casualty or emergency room unless the event meets one of the other criteria for being an SAE.
- With regard to the criteria for an important medical event, medical and scientific judgment should be used in deciding whether prompt reporting is appropriate in this situation.

7.2.1.6 Reporting of Serious Adverse Events

All SAEs occurring up to 30 days following completion of or discontinuation from the study must be reported to the sponsor, regardless of whether they are suspected of having a causal relationship with the study drug. Any SAEs for which the investigator does suspect a causal relationship must be reported to the sponsor regardless of the time elapsed since the last dose of the study drug.

Patients will be instructed to report SAEs to the investigator **within 24 hours**, by telephone. In turn, the investigator must report all SAEs to the sponsor **within 24 hours** of notification by the patient, using the sponsor’s SAE form. The sponsor will provide the contact information for reporting SAEs. An assessment of causality must be provided at the time of the initial report. The investigator or delegate must then complete and submit a follow-up SAE form to the sponsor **within 5 calendar days**, and must submit further follow-up forms if additional relevant follow-up information becomes available.

The sponsor will submit reports of SAEs to the appropriate regulatory agencies, in line with local regulatory requirements and timelines.

Investigators must report all SAEs to their IRB/IEC as well as to the sponsor. If any SAE that is considered at least possibly related to the study medication and is unexpected occurs at one site, the sponsor will promptly inform all other sites of this, and all investigators must then report this event to their own IRBs/IECs, following the same timelines as above or following local IRB/IEC policy, whichever takes precedence.

7.2.1.7 Follow-up and Documentation of SAEs

SAEs that occur during the study and up to 30 days after the last dose of study drug must be documented in the patient’s medical record and on the SAE report form. The investigator should attempt to establish a diagnosis of the event based on signs, symptoms, and/or other clinical information. In such cases, the diagnosis rather than the individual signs/symptoms should be documented as the SAE.

All SAEs must be followed until resolution, the condition stabilizes, the event is otherwise explained, or the patient is lost to follow-up. The investigator is responsible for ensuring that

follow-up includes any supplemental investigations that may be indicated, in order to elucidate the nature and/or causality of the SAE as completely as possible. This may include additional laboratory tests or investigations, histopathological examinations, or consultation with other health care professionals. The sponsor may request that the investigator perform or arrange for the conduct of supplemental measurements and/or evaluations.

If a patient dies during participation in the study or during a specified follow-up period, the sponsor should be sent a copy of any post-mortem findings, including histopathology.

New or updated information is to be recorded on the originally completed SAE report form, with all changes signed and dated by the investigator.

The CRA will verify the original SAE report form against the source documents at the monitoring visit.

7.2.1.8 Adverse Events of Special Interest

An important AE that has a known association with deferiprone is **neutropenia**, defined as an absolute neutrophil count (ANC) less than $1.5 \times 10^9/L$. The severity of neutropenia is categorized as follows:

Mild neutropenia:	A confirmed ANC $\geq 1.0 \times 10^9/L$ and $< 1.5 \times 10^9/L$.
Moderate neutropenia:	A confirmed ANC $\geq 0.5 \times 10^9/L$ and $< 1.0 \times 10^9/L$.
Severe neutropenia/agranulocytosis:	A confirmed ANC $< 0.5 \times 10^9/L$.

“Confirmed” means that the ANC has been found to be within the specified range on 2 consecutive measurements a maximum of 3 days apart. If both consecutive counts are below $1.5 \times 10^9/L$ but are not within the same range, a third count is required to determine the severity category. Neutropenia is considered to be resolved when ANC is $\geq 1.5 \times 10^9/L$ on 2 consecutive counts.

Management of Neutropenia

Patients will be scheduled for weekly hematology testing throughout the study, and the results will be forwarded to the investigator. If an ANC $< 1.5 \times 10^9/L$ is detected, the patient and, if possible, the primary care physician, are to be promptly notified. In addition, since both fever and infection can be associated with neutropenia, patients will be instructed to do the following:

- In the event of a temperature ≥ 38.5 °C/101.3 °F, they are to immediately discontinue treatment and contact the investigator at the 24-hour number provided. The investigator will request that CBC and differential count be obtained.
- If they develop any symptoms of infection, they are to promptly report this to the investigator at the 24-hour number provided. The investigator will then determine whether or not treatment should be interrupted.

The management of neutropenia depends on its severity, as described below.

Mild neutropenia:

- Instruct patient to interrupt deferiprone immediately.
- Repeat the ANC count daily until resolution.
- If possible, arrange for patient to be seen by a physician the same day for a physical examination, assessment of AEs, and a review of concomitant medications/therapies. If this is not possible, contact patient by phone to obtain information on AEs and medications.
- Advise patient to enter protective isolation, if possible.
- Notify the sponsor of the event by submitting the SAE form.
- If patient is not febrile and does not have an infection, deferiprone therapy can be re-initiated once 2 consecutive ANCs are $\geq 1.5 \times 10^9/L$ and it is deemed safe by the investigator. If patient is febrile and/or has an infection, therapy cannot be re-initiated until all symptoms have resolved.

Moderate neutropenia:

- Instruct patient to discontinue deferiprone immediately, and withdraw him/her from the study. If this occurs, arrange for the patient to return to the site for an early termination visit.
- Repeat the ANC count daily until resolution.
- If possible, arrange for patient to be seen the same day by a physician for a physical examination, assessment of AEs, and a review of concomitant medications/therapies. If this is not possible, contact patient by phone to obtain information on AEs and medications.
- If clinically indicated, arrange for patient to be admitted to hospital and undergo q4h measurement of vital signs. Otherwise, advise him/her to enter protective isolation and

have a family member obtain q4h temperature. If patient has fever $\geq 38.5^{\circ}\text{C}/101.3^{\circ}\text{F}$, arrange for him/her to be seen by a physician within 4 hours and to undergo an evaluation, including at least a blood culture. Antibiotics are to be initiated prior to obtaining the culture results, and are to be maintained until the patient becomes afebrile, the neutropenia has resolved, and blood cultures have been negative for a minimum of 72 hours. The antibiotics chosen should be based on local microbial prevalence and antibiotic sensitivity patterns. Broad spectrum antibiotics should be used in order to cover both gram negative and gram positive organisms.

- If possible, obtain blood sample for viral studies (CMV, parvovirus, and hepatitis A/B/C); serum ALT, BUN, and creatinine; and 10 mL of serum split into two 5 mL aliquots for frozen storage.
- Notify the sponsor of the event by submitting the SAE form.

Severe neutropenia/agranulocytosis:

- Instruct patient to discontinue deferiprone immediately, and withdraw him/her from the study.
- Repeat the ANC count daily until resolution.
- If possible, arrange for patient to be seen the same day by a physician for a physical examination, assessment of AEs, and a review of concomitant medications/therapies. If this is not possible, contact patient by phone to obtain information on AEs and medications.
- If possible, arrange for patient to be admitted to hospital and to have vital signs monitored q4h. Otherwise, advise him/her to enter protective isolation and have a family member obtain q4h temperature.
- If patient has fever $\geq 38.5^{\circ}\text{C}/101.3^{\circ}\text{F}$, arrange for him/her to be seen by a physician within 4 hours and to undergo an evaluation, including at least a blood culture. Antibiotics are to be initiated prior to obtaining the culture results, and are to be maintained until the patient becomes afebrile, the neutropenia has resolved, and blood cultures have been negative for a minimum of 72 hours. The antibiotics chosen should be based on local microbial prevalence and antibiotic sensitivity patterns. Broad spectrum antibiotics should be used in order to cover both gram negative and gram positive organisms.
- Contact the treating physician at the hospital and arrange or request for the following to be done, if possible:

- If possible, obtain blood sample for viral studies (CMV, parvovirus, and hepatitis A/B/C); serum ALT, BUN, and creatinine; and 10 mL of serum split into two 5 mL aliquots for frozen storage.
- Collect a blood sample for use in attempting to identify genetic or other biomarkers related to agranulocytosis (separate patient consent needs to be obtained).
- Obtain bone marrow aspirate for:
 - Histology
 - Progenitor culture
 - Frozen storage (1 mL sample)
- Obtain bone marrow biopsy (minimum length 3 mm).
- Perform septic work-up including chest x-ray and blood, urine, and throat cultures.
- If warranted, administer granulocyte stimulating factor, such as G-CSF 10 µg/kg, beginning the day that the ANC is confirmed as $< 0.5 \times 10^9/L$ and continuing daily until ANC is $\geq 1.5 \times 10^9/L$ on 2 consecutive days.
- If $ANC < 0.5 \times 10^9/L$ for 7 days, repeat bone marrow biopsy and aspirate weekly during the period of agranulocytosis, if warranted.
- Notify the sponsor of the event by submitting the SAE form.

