4.5.3 Treatment Interruptions

As in the initial study, patients will be provided with a card containing contact information for emergency services which they are to carry at all times, and will be advised to promptly report any symptoms indicative of infection such as fever or flu-like symptoms. Treatment will be interrupted under the following circumstances:

- If a patient develops an infection, therapy will be interrupted based on the investigator's judgment. If ANC $<1.5 \times 10^9/L$., neutrophil count must be obtained and monitored more frequently.
- If a patient develops a fever (defined as ≥ 38.5 °C or 101.3 °F), therapy must be interrupted immediately, and a CBC and differential count must be obtained.

Therapy with study medication can be re-initiated once all symptoms have been resolved and it is deemed safe by the investigator. See [Section 7.2.1.8](#), Adverse Events of Special Interest.

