- Remind the patient/authorized legal representative to do the following:
 - Return all study medication containers at the next visit, whether empty or unused
 - Keep careful track of adverse events and medication(s) used
 - Interrupt therapy immediately in the event of fever (temperature ≥ 38.5 °C/101.3 °F), and promptly report any symptoms indicative of infection such as fever or flu-like symptoms
 - If patient is on a regular dosing regimen of any of the medications listed in [Appendix 3](#) or of any other medication that has the potential to affect dystonia symptoms, to stay on the same regimen for the duration of the study. Any change in dose and dosing regimen should be limited to circumstances judged as absolutely necessary by the investigator.
 - If patient is being treated with any such medications on a PRN basis, to use them only under circumstances judged as absolutely necessary by the investigator, and to interrupt treatment prior to the next study visit according to the following timelines:

Medication	Treatment interruption period prior to current visit
Baclofen	30 days
Trihexyphenidyl	30 days
Clonazepam	30 days
Tizanidine	30 days
Botox	60 days
Tetrabenazine	90 days

- If patient has a DBS system or Baclofen pump in place, to make every effort to maintain the same DBS stimulation parameters or Baclofen pump settings for the duration of the study. Any changes in settings should be limited to circumstances judged as absolutely necessary by the investigator.
- If leaving the study before completion, to return to the clinic for an Early Termination Visit as soon as possible and no later than 30 days following the last dose of study medication
- Provide patient with card containing contact information for emergency services, and advise that this card should be carried at all times
- Schedule next study visit

Weekly Blood Draws (every 7 ± 3 days)

Note: These blood draws can be conducted either at a local laboratory or at the study site.

- Collect blood sample for hematology assessment. The results are to be reviewed by the investigator in a timely manner when they are received from the laboratory.

Telephone Contact (Week 1 ±2 days and Week 2 ±2 days)

A study staff member will contact the patient and/or legal representative by telephone at Week 1 and Week 2 with the following queries and reminders, and will document the responses:

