7.2.2 Laboratory Measurements

Samples for laboratory safety assessments will be taken at the time points indicated below. If a patient withdraws from the study, the End of Study procedures are to be performed at an early termination visit.

Hematology: Complete blood count (CBC), including total WBC, ANC, platelet count, and hemoglobin	Weekly
Blood chemistry: Serum ferritin, total protein, GGT, LDH, sodium, potassium, chloride, glucose, total, bilirubin, AST, ALT, albumin, blood urea nitrogen, calcium, creatinine, uric acid, alkaline phosphatase, and amylase	Visits 1, 2, 3, and 4
Urinalysis: pH, specific gravity, glucose, protein, ketones, and blood. If indicated by the dipstick, sediment microscopy will be performed.	Visits 1, 2, 3, and 4
Pregnancy testing: Serum pregnancy tests will be performed for all sexually active females of childbearing potential (unless the investigator determines there is no reasonable risk of pregnancy because of significant incapacity)	Visits 1, 2, 3, and 4

The investigator must review and interpret each laboratory report, and document the review by signing or initialing and dating the report. Any laboratory values that fall outside a clinically accepted range, or values that differ significantly from previous values, must be marked by the investigator as either “CS” (clinically significant) or “NCS” (not clinically significant). Any that are marked as CS must be further explained and documented as an AE.

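### Section 7.2.1.8 does not expressly order a deferiprone hold or a timed repeat count on a first ANC below 1.5 in a patient without fever or infection

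*Protocol*

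**What the plan says.** All places are in the protocol; ANC values are × 10⁹/L.

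- **Grading (7.2.1.8).** Neutropenia is introduced as an ANC below 1.5. The mild (1.0 to below 1.5), moderate (0.5 to below 1.0) and severe (below 0.5) grades each need a confirmed ANC, which "means that the ANC has been found to be within the specified range on 2 consecutive measurements a maximum of 3 days apart". If two consecutive low counts "are not within the same range, a third count is required to determine the severity category".
- **Management (7.2.1.8).** When an ANC below 1.5 "is detected, the patient and, if possible, the primary care physician, are to be promptly notified". The section later adds: "The management of neutropenia depends on its severity, as described below". The mild heading orders interruption; the moderate and severe headings order discontinuation and withdrawal from the study. All three order daily counts.
- **Fever and infection (7.2.1.8).** A temperature of 38.5 °C or more stops the drug at any ANC. Symptoms of infection go to the investigator, who decides on interruption.
- **Routine counts (5.1 and 7.2.2).** The schedule is "Weekly Blood Draws (every 7 ± 3 days", with timely review of results. Section 7.2.2 adds: "The investigator must review and interpret each laboratory report", and abnormal values are marked clinically significant or not.
- **Interruptions (4.5.3).** "If a patient develops an infection, therapy will be interrupted based on the" investigator's judgment. In the same bullet, at an ANC below 1.5, the "neutrophil count must be obtained and monitored more frequently".

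**The concern.** The instruction that matters most is what a site does on the day one low count comes back. At that moment the patient has no grade, because a grade needs two counts. Taken literally, the stop and daily-count orders do not yet apply, and the only express duty is to tell the patient and, where possible, the primary care physician.

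Section 1.3 names agranulocytosis as the most serious adverse event associated with deferiprone. It says the condition usually resolves when the drug is stopped, and that deaths have been reported after marketing. The timing of the stop is therefore a main safeguard. On the literal reading, dosing may continue while agranulocytosis is suspected but unconfirmed, and sites could reasonably handle the same first low count in different ways.

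**Working it through.** The plan states no figure on this point, so there is none to reproduce. The check is a reading of the text plus interval arithmetic.

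**1. Which text covers a first ANC below 1.5 with no fever or infection?**

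| Place | What it orders | Hold? | Timed repeat? |
|---|---|---|---|
| 7.2.1.8, on detection | Notification | No | No |
| 7.2.1.8, grade headings | Stop and daily counts | Only once graded | Only once graded |
| 7.2.1.8, discordant low counts | Third count | Not stated | No deadline |
| 4.5.3, infection bullet | More frequent counts | Investigator's judgment, for infection | No interval |
| 5.1 and 7.2.2 | Review and marking of the result | No | No |
| 7.2.1.2 | Follow-up of adverse events, including a count marked clinically significant | No | No deadline |

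**2. Can the routine schedule confirm?** Inputs: 7 ± 3 days (5.1) and a confirmation limit of 3 days (7.2.1.8).

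- With ± 3 days as the interval between draws, the gap is 7 − 3 = 4 to 7 + 3 = 10 days. That is 4 − 3 = 1 to 10 − 3 = 7 days beyond the limit.
- With ± 3 days as a window around fixed weekly dates, the gap is 7 − 6 = 1 to 7 + 6 = 13 days. An early draw could then fall within 3 days, but the nominal 7-day gap still does not.

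Either way, routine draws are not designed to confirm. An extra draw is needed, and no sentence orders one within a stated time for this patient.

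**3. Doses before a mandated stop.** Dosing is twice a day (6.1.1).

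- Detection reading: 0 doses.
- Literal reading, nothing done until the next routine draw, interval reading: 2 × 4 = 8 to 2 × 10 = 20 doses; 2 × 7 = 14 at the nominal gap.
- Literal reading with an extra draw: it depends on when that draw is taken.

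**4. What a hold would cost.** Scheduled doses per patient are 78 weeks × 7 days × 2 = 1,092. Result turnaround is not given, so it is an assumption.

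| Turnaround | Hold | Doses missed | Share of 1,092 |
|---|---|---|---|
| Same day | about 2 days | 4 | 0.37% |
| 1 day extra | about 3 days | 6 | 0.55% |
| 2 days extra | about 4 days | 8 | 0.73% |

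**5. Fever wording.** The Visit 1 reminder and the Week 1 and 2 telephone calls (5.1), Section 4.5.3 and Section 7.2.1.8 all stop the drug at 38.5 °C or more. The Visit 2/3 reminder in 5.1 instead tells patients to interrupt for infection and lists fever only as something to report. Sections 4.5.3 and 7.2.1.8 leave interruption for infection to the investigator.

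**The case against.** The best answer is that the section can be read as stopping the drug at detection. Its opening definition of neutropenia does not mention confirmation, the management text starts from detection, every grade stops the drug immediately, and the confirmation and third-count rules presuppose a prompt repeat. Confirmation would then decide only between a resumable interruption and permanent withdrawal. In support, the G-CSF instruction is expressly tied to the day of confirmation, while the stop orders are not.

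This reading is workable and may be what was meant, but it is not written down. It also has a difficulty: the moderate and severe headings join discontinuation to withdrawal in one instruction, so applying them at detection would withdraw a patient on a single unconfirmed ANC below 1.0. The G-CSF wording is weak evidence either way, because it sits under a heading that already requires confirmation.

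A second answer is that Section 7.2.1.2 makes follow-up mandatory for an abnormal count marked clinically significant, including any further tests needed. That stands, and it means the patient is not left without follow-up. It sets no deadline and no hold. Investigators may also reduce the dose (3.3) or withdraw the patient (4.5) at any time, but that is discretion rather than a common rule.

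The fever-reminder mismatch is a separate and smaller matter. Febrile patients are still told at Visits 2 and 3 to report at once, and the mismatch adds no weight to the ANC point.

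**Conclusion.** The point holds as an ambiguity in a safety instruction. Section 7.2.1.8 gives no express hold and no timed repeat on a first ANC below 1.5 in a patient without fever or infection, and the other sections do not supply them.

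A reader might infer three stronger things that the documents do not support:

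- **That exposure is capped at 3 days, or 6 doses.** The 3-day limit defines what counts as confirmed; it does not oblige anyone to draw the second count. The range is 0 doses on the detection reading and, on the literal reading, whatever the timing of an unordered repeat makes it. The 8 to 20 figure assumes that nothing happens before the next routine draw and that ± 3 days is the interval between draws.
- **That the schedule can never confirm.** This holds on the interval reading, but not strictly if ± 3 days is a window around fixed dates.
- **That patients were or would be left on drug.** The text permits different practice; it does not show that any occurred. How often a first low count arises in this population cannot be derived. The 1.7% in Section 1.3 is agranulocytosis in pooled clinical trials, not first low counts in PKAN.

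It is a cheap improvement, held with medium confidence because a workable reading exists.

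**What to change.** In 7.2.1.8, state that:

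1. any single ANC below 1.5 triggers an immediate hold and a repeat count within 24 hours, then daily counts until the event is classified or resolved (two consecutive counts of at least 1.5, as already defined);
2. the hold continues while discordant low counts await a third count, taken the next day;
3. confirmation is used only for grading and permanent withdrawal.

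In 4.5.3, add an ANC below 1.5 to the circumstances for interruption, keeping the existing cross-reference to 7.2.1.8. Separately, in 5.1, give the Visit 2/3 reminder the Visit 1 content: stop at once at 38.5 °C or more, and report symptoms of infection promptly.

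The cost is a wording amendment and a site memo, with no new study visits. Each isolated low value would bring about 2 extra local counts and a hold of about 2 to 4 days, depending on turnaround. Some of those holds will prove unnecessary, which is the price of a uniform rule.
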